Statistical analysis: We will use linear conditional regression to explore which parameters of sports participation, HAL scores, and domain scores of HEP-Test-Q best explain the variation in bleeding frequency and joint function. Analyses will be adjusted for age and haemophilia severity.

6.2 To assess the health-related quality of life of PWH in the Netherlands

6.2.1 General quality of life

Primary objective 1: To describe health-related quality of life of PWH in the Netherlands over time since 1992.

Study design and population: A dynamic cohort design will be used. All haemophilia patients who filled out the RAND -36 questionnaire in 1992, 2001 and in the current study will be included. **Determinant:** disease severity, calendar time and age.

Endpoint: We will use the RAND-36 (adults) and the CHO-KLAT (children) to evaluate overall healthrelated quality of life.

Statistical analyses: Descriptive statistics will be used. We will conduct a repeated measurements analysis with the results of the previous HiN-studies from 1992 and 2001 using the RAND-36. We will also compare our results with the general male population using the RAND-36.

Primary objective 2: To quantify the association between health-related quality of life and disease

severity, presence of comorbidities, past and current presence of inhibitors, degree of self-reported joint health status, bleeding phenotype, pain, joint function, treatment type and ability to self-manage in patients with mild, moderate and severe haemophilia.

Study design and population: Cross-sectional. The total population will consist of all PWH in the Netherlands.

Determinant: Disease severity (mild, moderate or severe), the self-reported number of bleeds that required medical treatment in the previous year, ability to self-manage and the degree of arthropathy will be used as the determinants. Ability to self-manage will be assessed with the validated PAM-13 questionnaire (adults) and the HSES (children). Other determinants will be obtained using a questionnaire and/or extracted from electronic medical records. Endpoint: We will use the RAND-36 (in adults) and the CHO-KLAT (in children) as the endpoint. Statistical analysis: Multiple linear regression will be used to assess these associations. Subgroup analyses will be performed for PWH aged >50 years.

Primary objective 3: To investigate the relationships between health-related quality of life and the prevalence of social determinants of health, including participation and social functioning, ability to work, education and relationships in older adults (>50 years of age) with haemophilia, and compare with 2001.

Study design and population: cross-sectional design in adult population >50 years of age and dynamic cohort of people who filled in the questionnaire in 2001.

Determinant: Disease status and severity, age, social determinants of health (such as socioeconomic status, social participation). Information on determinants will be obtained from the questionnaire.

Endpoint: HRQoL, as measured with the RAND-36

Statistical analyses: linear regression analyses will be performed.

Primary objective 4: To assess the incidence of falls and the prevalence of fear of falling in older adults (>50 years of age) with haemophilia.

Study design and population: Cross-sectional design in adults >65 years of age. Fear of falling will be assessed using the modified FES questionnaire. Falls history will be obtained from the patient's medical record.

Determinant: Age, disease severity, use of walking aid, previous joint replacement surgery and falls history.

Endpoint: Fear of falling as measured with the FES questionnaire and falls history.

Statistical analyses: Descriptive statistics will be used.

Primary objective 5: To assess the incidence of a false-positive result of the self-administered faeces test in the colon cancer screening program in adults with haemophilia between 55 and 75 years of age.

Study design and population: cross-sectional design in adults between 55 and 75 years of age who participated in the voluntary colon cancer screening program.

Determinant: disease status

Endpoint: positive result on the self-administered faeces test of the colon cancer screening program. This information will be obtained from the questionnaire.

Statistical analyses: descriptive statistics will be used to assess the incidence of a positive test result.

Primary objective 6: To assess the incidence of abnormal results of the additional colonoscopy in people with haemophilia compared to the general population.

Study design and population: cross-sectional design in adults between 55 and 75 years of age who participated in the voluntary colon cancer screening program and underwent an additional colonoscopy.

Determinant: disease status

Endpoint: positive result on the colonoscopy. This information will be obtained from the medical record.

Statistical analyses: descriptive statistics will be used to assess the incidence of a positive colonoscopy.

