2.2.1 General quality of life

Main objectives:

- 1. To describe health-related quality of life in all PWH in the Netherlands over time since 1992.
- To quantify the association between health-related quality of life and disease severity, degree of arthropathy, bleeding phenotype, pain and pain coping, self-reported joint function and ability to self-manage in patients with mild, moderate or severe haemophilia.
- To quantify the relationships between health-related quality of life and the prevalence of social determinants of health, including participation and social functioning, ability to work, education and relationships patients with haemophilia. These study questions will also be separately assessed in the older population (>50yr)
- 4. To assess the incidence of falls and the prevalence of fear of falling in older adults (>65 years of age) with haemophilia.
- 5. To assess the incidence of a false-positive result of the self-administered faeces test in the colon cancer screening test in adults with haemophilia between 55 and 75 years of age.
- 6. To assess the incidence of abnormal results of the additional colonoscopy in people with haemophilia compared to the general population.

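### Objective 3 on social determinants and quality of life covers patients in general in section 2.2.1 but only adults over 50 in section 6.2.1, so the planned cross-sectional analysis gives no estimate at age 50 or younger

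*Protocol*

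**What the plan says.** Section 2.2.1, main objective 3, concerns the relationship between health-related quality of life and social determinants, including "ability to work, education and relationships patients with haemophilia". No age limit is given. The next sentence adds: "These study questions will also be separately assessed in the older population (>50yr").

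Section 6.2.1, primary objective 3, restates the objective for "education and relationships in older adults (>50 years of age) with haemophilia, and compare with 2001". Its design line reads "cross-sectional design in adult population >50 years of age and dynamic cohort of people who filled in the questionnaire in 2001". The determinants are "Disease status and severity, age, social determinants of health (such as socioeconomic status, social participation"), the endpoint is "HRQoL, as measured with the RAND-36", and the analysis is linear regression. The comparison with 2001 appears here but not in objective 3 of 2.2.1.

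**The concern.** The objectives chapter presents the over-50 analysis as an addition to an analysis of patients in general. The substudy chapter keeps only the addition. An analyst works from chapter 6, because that is where population, determinants, endpoint and method are set. That analyst would fit the regression in adults over 50 and stop, and a stated main objective would have no result for younger patients.

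The protocol gives its own reasons for wanting the wider picture. Section 1.0 says that haemophilia may affect schooling and career. Section 1.2.1 says that no recent comprehensive account of these social factors exists for the Dutch haemophilia population. A sample restricted to those over 50 cannot supply that account.

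**Working it through.** No sample-size, power or error-rate figure is involved, so the check is a comparison of text. The one size statement, in section 4.4, is 1800 × 0.70 = 1260 expected respondents. It is arithmetically right but is not broken down by age, so it does not bear on the point.

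**Step 1. Scope of objective 3 in the two chapters.**

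| Element | Section 2.2.1 | Section 6.2.1 |
|---|---|---|
| Population | Patients with haemophilia, no age limit | Cross-sectional: adults over 50; plus a cohort of 2001 respondents |
| Over-50 group | Additional, separate assessment | The whole cross-sectional population |
| Comparison with 2001 | Not mentioned | Included |
| Endpoint | Health-related quality of life | RAND-36 only |

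The populations differ, and the added subgroup has become the only cross-sectional analysis.

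**Step 2. Does another objective fill the gap?**

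- 6.2.1 objective 1 describes quality of life by severity, calendar time and age. It has no social determinants.
- 6.2.1 objective 2 covers all patients, but its determinants are severity, number of treated bleeds, "ability to self-manage and the degree of arthropathy will be used as the determinants". Its objective sentence adds items such as comorbidities, inhibitors, pain and treatment type. Participation, work, education and relationships are not among them.
- 6.2.1 objectives 4 to 6 concern falls and colon cancer screening.
- Section 6.3.2 uses absence from work or school, but as a determinant of bleeds, not of quality of life.

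None of these closes the gap.

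**Step 3. Does the 2001 cohort fill it?** The design line gives this cohort no age limit of its own, so it might include some people aged 50 or younger. It stands under an objective worded for those over 50, it serves the comparison with 2001, and it contains only people who answered in 2001. It does not amount to a cross-sectional analysis of current patients of all ages.

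**Step 4. Are the data available?** Yes. Section 5.1.1 lists socio-economic characteristics and the RAND-36 in the adult questionnaire, and Appendix 3 assigns the RAND-36 to adults from age 18. Children answer the CHO-KLAT instead, so an objective with the RAND-36 as its sole endpoint cannot cover them, although 2.2.1 does not exclude them.

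**Step 5. Which structure fits the rest of the plan?** For objective 2, section 6.2.1 analyses the whole population and adds a subgroup over 50. That is the structure 2.2.1 describes for objective 3. Objective 4 also carries inconsistent age limits: over 65 in 2.2.1, but worded for over 50 with a population over 65 in 6.2.1. This makes a drafting slip plausible without proving one.

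**The case against.** The restriction may be deliberate. Section 1.2.1 says that adverse social factors are more common in the older generation because of poorer treatment in the past, and 1.2.2 says that the needs of ageing patients are largely unknown. Narrowing 2.2.1 to those over 50 would remove the contradiction just as well. The analysis is one exploratory regression in a large observational survey, with no power claim attached. The data are collected regardless, so nothing is lost for good.

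Much of this stands. It shows why an over-50 analysis is worth having and why the matter is not grave. It does not explain why 2.2.1 makes that analysis an addition, and narrowing 2.2.1 would give up a stated main objective whose data will be in hand.

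A reader might go further than the documents allow in three ways:

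- *That these determinants matter most in men of working age, who are left out.* Nothing in the protocol says so. Section 1.2.1 points the other way on prevalence, and many people over 50 are of working age.
- *That the introduction calls for contrasting the older generation with those raised on modern prophylaxis.* Sections 1.2.1 and 1.2.2 explain why older patients fare worse, but they set no such contrast as an objective. The comparison that 6.2.1 names is with 2001.
- *That no model at all would include anyone aged 50 or younger.* The unclear age range of the 2001 cohort prevents so absolute a statement.

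**Conclusion.** The inconsistency is real. Followed as written, the cross-sectional analysis in 6.2.1 leaves objective 3 of 2.2.1 unanswered for patients aged 50 or younger, and no other planned analysis supplies the answer. This rests on the plain reading that the over-50 assessment in 2.2.1 comes on top of an analysis in patients generally.

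No numerical size applies. A reader might want to express the harm as wider confidence intervals, but the protocol does not give the share of respondents over 50, and precision is not the issue. If the association varies with age, the over-50 and all-adult coefficients are different quantities, and the over-50 estimate is equally precise whether or not the wider analysis is run. What is missing is an estimate.

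The point should be corrected before analysis. It does not threaten data collection.

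**What to change.** - In 6.2.1, primary objective 3, set the cross-sectional population to all adults with a completed RAND-36, and name over 50 as a separate subgroup specified in advance, as objective 2 does. An age interaction term is optional, since 2.2.1 promises only a separate assessment.
- State the age range of the 2001 comparison cohort, which the present design line leaves open.
- In 2.2.1, say that objective 3 covers adults, because the RAND-36 is its only endpoint, and mention the comparison with 2001 so that the two sections match.

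If the sponsor did intend only those over 50, 2.2.1 should say so and give the reason.

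The cost is protocol wording and one more regression. No new data are needed.

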6.2.2 Sexuality

Primary objectives: To assess the incidence of hematospermia in PWH and to describe the presence of limitations in sexual health due to haemophilia in PWH.

Study design and population: a cross-sectional design will be used to assess hematospermia and limitations in sexual health in all adults with haemophilia A or B. Information will be obtained with the questionnaire.

Determinant: disease status and severity

Endpoint: self-reported hematospermia, self-reported limitations in physical sexual functioning.Statistical analyses: Descriptive statistics will be used.

6.3 To assess quality of care of PWH in the Netherlands

6.3.1 General quality of care

Primary objective 1: To assess quality of care from a patient's perspective, including information provision, communication with care providers and financial consequences of health care services use.

Study design and population: A cross-sectional study design will be used.

Determinant: disease status and severity

Endpoint: Quality of care as represented by satisfaction with provided treatment, accessibility and availability of care, information provision and communication.

Statistical analyses: Descriptive statistics will be used.

Primary objective 2: To assess treatment satisfaction of PWH.
Study design and population: A cross-sectional study design will be used. Information about treatment will be obtained from the Hemo-SAT questionnaire.
Determinant: disease status and severity
Endpoint: treatment satisfaction according to the Hemo-SAT questionnaire.
Statistical analysis: Descriptive statistics will be used.

6.3.2 Transition

Primary objective 1: To compare adherence in adolescents and young adults with severe haemophilia to adherence in other age groups.
Study design and population: A cross-sectional study design will be used. Adolescents and young adults (15-25 years of age) with severe haemophilia A and B.
Determinant: Age
Endpoint: Adherence, as measured with the validated VERITAS-pro questionnaire.
Statistical analyses: Descriptive statistics will be used.

Primary objective 2: To assess the relationship between self-efficacy, treatment adherence and self-reported readiness for transition in adolescents and young adults with severe haemophilia.Study design and population: A cross-sectional study design will be used. 'Readiness for transition'

in adolescents before transition will be measured with a single question. Self-efficacy will be measured with the haemophilia-specific self-efficacy scale (HSES). **Determinant:** age, self-efficacy, health-related quality of life **Endpoint:** readiness for transition.

Statistical analyses: Linear regression will be used to explore factors that explain readiness for transition.

Secondary objective 1: To assess the relationship between adherence, factor use, absence from work or school and bleeding outcomes in young adults with severe haemophilia.

Study design and population: A cross-sectional study design will be used. Adherence will be assessed with the VERITAS-pro questionnaire. Other information will be obtained from the questionnaire.

Determinant: age, adherence, factor use, absence from work or school

Endpoint: number of bleeds

Statistical analyses: Linear regression will be used to explore factors that explain readiness for transition.

6.3.3 Desmopressin use

Primary objective 1: To assess desmopressin use, side effects, barriers for use and information provision by clinicians

Study design and population: A cross-sectional design will be used. All patients with moderate or mild haemophilia A will answer questions about desmopressin use

Determinant: mild or moderate haemophilia A.

Endpoint: Use of desmopressin, (perceived) side effects, barriers for use and information provision by clinicians

Statistical analyses: Descriptive statistics will be used.

6.3.4 New treatment options for haemophilia

Primary objective 2: To assess patients' perceptions of new treatment options (gene therapy, extended half-life clotting factors, non-replacement coagulation factor therapies and tailored prophylaxis by using pharmacokinetic dosing) and factors that may explain these perceptions, such as age and disease severity.

Study design and population: A cross-sectional design will be used.
Determinant: disease status and severity, age
Endpoint: attitude towards new treatment options
Statistical analyses: Descriptive statistics will be used. Results will be compared to patients' opinions on these topics in 2001.

6.3.5 Needle fear

Primary objective 1: To assess the prevalence of needle fear or needle phobia among PWH.Study design and population: A cross-sectional design will be used. The questionnaire contains questions about needle fear and symptoms.

Determinant: disease status and severity, treatment method (prophylaxis, on-demand), age.

Information on these determinants will be obtained from the questionnaire.

Endpoint: self-reported fear of needles

Statistical analyses: Descriptive statistics will be used.

Secondary objective 1: To assess the relationship between needle fear and adherence in patients with severe haemophilia.

Determinant: needle fear

Endpoint: Adherence (as measured with the VERITAS-pro questionnaire),

Statistical analysis: Linear regression analysis will be used to assess to what extent adherence is explained by needle fear.

6.4 Studies elucidating the variability in clinical phenotype among PWH

6.4.1 To assess the usefulness of The Calibrated Automated Thrombogram (CAT) assay in relation to clinical phenotype.

Primary objective 1: To establish specific sample conditions to generate reliable CAT assay outcome parameters in patients with haemophilia.

Study design and population: In vitro spiking experiments will be used to establish specific sample conditions to generate reliable CAT assay outcome parameters. Thrombin Generation (TG) in FVIII or FIX deficient plasma is determined after in vitro suppletion of FVIII or FIX in final activity of 5%, 10%, 15%, 20%, 25%, 30%, 35%, 40%, 45% and 50% to establish maximum TG parameters. Optimal TG

HiN-6 study

conditions are studied by varying the amount of TF: 5pM, 1pM and 0,5 pM. Final phospholipid concentration is set at 4 uM. Cases will consist of 25 severe haemophilia patients, 25 moderate haemophilia patients and 25 mild haemophilia patients. Controls will consist of 25 healthy patients without haemophilia and no personal or family history of thrombosis or bleeding disorders and no relevant medication.

Secondary objective 1: To assess the association between the results of the CAT assay and the self-reported clinical bleeding phenotype of patients with severe, moderate and mild haemophilia.
Study design and population: A cross-sectional study design will be used. The population will consist of 25 severe haemophilia patients, 25 moderate haemophilia patients and 25 mild haemophilia patients.

Determinant: The following parameters of the CAT assay will be used as the determinant; lag-time, time to peak, peak height and endogenous thrombin potential.

Endpoint: The modified bleeding severity score developed by Schulman et al [97] will be used as the endpoint (see paragraph 5.1.3).

Statistical analysis: The association between each parameter of the CAT assay (lag-time, time to peak, peak height and endogenous thrombin potential) and bleeding severity will be assessed using linear regression.

Secondary objective 2: To evaluate if the CAT assay can accurately diagnose the self-reported clinical bleeding phenotype of patients with severe, moderate and mild haemophilia.

Study design and population: A cross-sectional study design will be used. The population will consist of 25 severe haemophilia patients, 25 moderate haemophilia patients and 25 mild haemophilia patients.

Determinants: The following parameters of the CAT assay will be used as determinants; lag-time, time to peak, peak height and endogenous thrombin potential. FVIII concentration (measured using the chromogenic assay) will also be used as a determinant.

Endpoint: The modified bleeding severity score developed by Schulman et al [97] will be applied to this study population (see paragraph 5.1.3) and used as a dichotomous outcome. Mild bleeders will be defined as being in the lowest two quartiles of the modified bleeding severity score, severe bleeders will be defined as being in the highest two quartiles of the modified bleeding severity score. **Statistical analysis:** The CAT assay parameters and FVIII concentration will be used to predict if a patient is a mild or a severe bleeder (based on the modified bleeding severity score). We will quantify diagnostic performance by constructing ROC-curves for each parameter of the CAT assay

and for FVIII concentration. We will then test if the AUROC of each parameter of the CAT assay differs significantly from the AUROC of the chromogenic assay. This analysis will be performed for the total population and separately for each category of severity.

6.4.2 To assess the usefulness of the Nijmegen Haemostasis Assay (NHA) in relation to clinical phenotype:

Primary objective 1: To assess the association between the results of the NHA and the self-reported clinical bleeding phenotype of patients with severe, moderate and mild haemophilia A and B.
Study design and population: A cross-sectional study design will be used. The population will consist of all haemophilia A and B patients in the Netherlands.

Determinant: The following parameters of the NHA will be used as determinants; lag-time, thrombin peak-time, thrombin peak-height, area under the curve (AUC), fibrin lysis time (FLT), plasmin peak-height and plasmin potential.

Potential confounders: FVIII/FIX genotype, VWF antigen levels and VWF activity.

Endpoint: The modified bleeding severity score developed by Schulman et al [97] will be used as the endpoint (see paragraph 5.1.3). **Statistical analysis:** The association between each parameter of the NHA and bleeding severity will be assessed using linear regression.

Primary objective 2: To evaluate if the NHA can accurately diagnose the self-reported clinical bleeding phenotype of patients with severe, moderate and mild haemophilia.

Study design and population: A cross-sectional study design will be used. The population will consist of all haemophilia A and B patients in the Netherlands.

Determinants: The following parameters of the NHA will be used as determinants; lag-time, thrombin peak-time, thrombin peak-height, area under the curve (AUC), fibrin lysis time (FLT), plasmin peak-height and plasmin potential. FVIII concentration (measured using the chromogenic assay) will also be used as a determinant.

Other potential predictors of clinical bleeding phenotype: FVIII/FIX genotype, VWF antigen levels and VWF activity.

Endpoint: The modified bleeding severity score developed by Schulman et al [97] will be applied to this study population (see paragraph 5.1.3) and used as a dichotomous outcome. Mild bleeders will be defined as being in the lowest two quartiles of the modified bleeding severity score, severe bleeders will be defined as being in the highest two quartiles of the modified bleeding severity score. **Statistical analysis:** Firstly, we will perform univariate logistic regression using FVIII concentration as

the determinant (the basic prediction model). To quantify the incremental value of the NHA parameters, they will be added to the basic prediction model to create the full prediction model. For internal validation, bootstrapping techniques will be used to reduce overfitting. Agreement between observed and predicted outcomes will be assessed using a calibration plot. Discrimination will be assessed by calculating the AUROC of the full model. The added value of the NHA will be assessed by comparing the AUROC of the basic model (only FVIII concentration) with the AUROC of the full model (FVIII concentration + NHA parameters).

6.4.3 To assess misclassification of disease severity by the one-stage clotting assay in haemophilia B patients:

Primary objective 1: To assess the extent of discrepancy in FIX activity level as measured by the one stage clotting assay to the chromogenic assay in patients with mild and moderate haemophilia B.
Study design and population: A cross-sectional study design will be used. The population will consist of all persons with mild and moderate haemophilia B.

Determinant: FVIII activity level, as determined by the chromogenic assay.

Endpoint: FVIII activity level, as defined using the one-stage clotting assay.

Statistical analysis: This objective will firstly be explored using descriptive statistics. Furthermore, using the chromogenic assay as the reference test, we will calculate sensitivity and specificity (with corresponding 95%Cl's) for the one-stage clotting assay.

Primary objective 2: To evaluate the association between F9 genotype and discrepancy between the FIX activity levels as measured by the one-stage clotting assay and the chromogenic assay in patients with mild and moderate haemophilia B.

Study design and population: A cross-sectional study design will be used. The population will consist of all persons with mild and moderate haemophilia B.

Determinant: F8 and F9 genotype are the determinants. Information on F8/F9 genotype will be obtained from each patient's medical record.

Endpoint: A large discrepancy between the result of the one-stage clotting assay (FVIII: C_{1st}) and the result of the chromogenic assay (FVIII: C_{chr}) will be used as the endpoint. A large discrepancy between the result of the one-stage clotting assay and the chromogenic assay is defined as having a ratio of FVIII: C_{chr} to FVIII: C_{1st} lower than 0.6.

Statistical analysis: The association between F8/F9 genotype and a discrepancy between the results of the one-stage clotting assay and the chromogenic assay will be assessed using logistic regression.

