1.1 Describing the health status of the Dutch haemophilia population

1.1.1 45 years of haemophilia treatment in the Netherlands, 1972-2017

Before the mid-1960s, PWH commonly died due to haemorrhages because no treatment was available. Later, many PWH died of the consequences of HIV or HCV infection caused by the use of

¹ In 2017, two academic treatment centres (Radboud University Medical Centre and Maastricht University Medical Centre) will merge with a general hospital (Máxima Medisch Centrum Eindhoven) to become one treatment centre, resulting in a total of six haemophilia treatment centres.

contaminated blood products in the 1980s and 90s. However, haemophilia care has greatly advanced over the years. The implementation of viral inactivation techniques has practically eliminated the risk of HIV or HCV infection. In addition, the introduction of prophylaxis has greatly reduced the number of bleeds and bleeding-induced joint damage. The improvement in treatment is reflected in patients' increasing life expectancy, which is currently approaching that of the general population. As a consequence, age-related co-morbidities are becoming more prevalent.[1] In recent years, there has also been more attention for other health outcomes in haemophilia, including pain (and coping with pain) and mental health. [7, 11, 12] The HiN-6 study will evaluate the impact of these medical developments on the health outcomes of the entire Dutch haemophilia population. We will achieve this by evaluating changes in the prevalence of (joint) bleeds, clotting factor consumption, inhibitor formation and HIV/HCV infection. In addition, we intend to describe the prevalence of the most important co-morbidities associated with haemophilia, including cardiovascular disease (CVD), obesity, physical activity, cancer, liver disease, chronic kidney disease (CKD), diabetes, osteoporosis and chronic pain.

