1.4.1 The Calibrated Automated Thrombogram (CAT) assay

The Calibrated Automated Thrombogram (CAT) assay as developed by Hemker et al [59] is a modified thrombin generation assay. Thrombin generation is calculated from the splitting of a fluorogenic substrate, which is calibrated against a sample with a known thrombin activity. The resulting thrombogram reflects the overall function of blood coagulation, balancing between both

pro-coagulant and anti-coagulant factors. The original thrombin generation assay is influenced by many pre-analytical variables (e.g. drawing of sample, sample handling time, temperature, colour of the plasma) as well as by critical analytical procedures (type of substrate, so called inner filter effect, need for calibration per sample). The CAT assay has standardized most of these aspects. However, interlaboratory comparison of CAT assays remains troublesome because of differences in substrates used. The CAT assays can be adapted by using different activators (TF or FIXa), different concentrations of activators, different sources (platelet rich plasma, platelet poor plasma, whole blood samples) or by adding various compounds (phospholipids, corn trypsin inhibitor to prevent contact activation).

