4.1 Population

All male Dutch patients with severe, moderate, or mild haemophilia A or B who are registered as such at one of the seven haemophilia treatment centres in the Netherlands will be eligible for inclusion. In addition, currently deceased patients that participated in the HiN-5 questionnaire in 2001 will also be eligible for inclusion. Severe haemophilia A or B is defined as having FVIII or FIX levels <0.01 IU/ml, moderate haemophilia A or B is defined as having FVIII or FIX levels between 0.01-0.05 IU/ml and mild haemophilia A or B is defined as having FVIII or FIX levels >0.05-0.40 IU/ml.

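### The stated confounder list for the NHA association analysis (6.4.2, primary objective 1) leaves out treatment centre, which is already recorded and could affect both the assay value and the bleeding score

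*Protocol*

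**What the plan says.** The protocol sets its adjustment variables objective by objective. For the NHA association analysis (section 6.4.2, primary objective 1) the list reads "Potential confounders: FVIII/FIX genotype, VWF antigen levels and VWF activity". The analysis is one line: "The association between each parameter of the NHA and bleeding severity will be assessed using linear regression". The population is all Dutch haemophilia A and B patients.

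The sampling is multicentre. Eligible patients are those "registered as such at one of the seven haemophilia treatment centres in the Netherlands", and a footnote in section 1.1.1 expects a merger "resulting in a total of six haemophilia treatment centres". Section 5.1.2 has the blood drawn at a regular visit to the treatment centre. Both the case report form (Appendix 1) and the sample collection form (Appendix 2) have a field for centre.

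The endpoint is defined in section 5.1.3. It is the sum of two components, each scaled to run from 0 to 1: the annual joint bleed rate, and annual factor consumption per kilogram of body weight.

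On sample handling, section 1.4.1 states: "The original thrombin generation assay is influenced by many pre-analytical variables (e.g. drawing of sample, sample handling time, temperature", among other influences. It goes on to say that the CAT has standardised most of these, and puts the remaining difficulty of comparing laboratories down to substrates. Section 1.4.2, on the NHA, says nothing about pre-analytical influences or their standardisation.

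**The concern.** A variable that shifts the assay value for reasons unrelated to the patient acts as measurement error in the determinant and flattens the regression slope. A variable that also shifts the bleeding score is a confounder and can create an association where none exists.

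Centre could do either. It could affect the NHA value through differences in drawing or handling. It could affect the score through factor consumption, which depends on how intensively patients are treated as well as on how readily they bleed. The sample form, as shown, records the last infusion, product, dose, weight and height, but neither time from draw to processing nor temperature. Centre is therefore the only visible stand-in for handling differences.

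At stake is a primary objective of this substudy: whether the NHA reflects the clinical bleeding phenotype, and how strongly.

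**Working it through.** **Inputs from the protocol**
- Expected participants: 1800 × 0.70 = 1260 (section 4.4), which reproduces the stated figure. It is an upper bound for the NHA, because blood sampling is voluntary (section 5.1.2).
- Centres: 7 (section 4.1).
- CAT sample: "25 severe haemophilia patients, 25 moderate haemophilia patients and 25 mild haemophilia" patients, so 25 × 3 = 75 (section 6.4.1).
- No power, effect size or detectable difference is stated for the NHA or CAT regressions, so there is none to reproduce.

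**Assumptions, because the protocol gives no figures**
- Share of NHA variance due to centre, ρx: 0 to 0.20.
- Share of bleeding-score variance due to centre, ρy: 0 to 0.10.
- Seven centres of equal size, two-sided 5% test, correlation 0.3 where an association is simulated.
- n = 900 as a lower NHA sample size. This is not in the protocol; 900/1260 = 71% of respondents giving a usable sample.

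**Step 1: dilution, when centre affects the assay but not the score.** With K = 7 sampled centres, the observed between-centre variance averages 6/7 of ρx. The ratio of unadjusted to adjusted slope is therefore about (1 − ρx) / [(1 − ρx) + (6/7)ρx].
- ρx = 0: 1.00
- ρx = 0.05: 0.95 / (0.95 + 0.043) = 0.957
- ρx = 0.10: 0.90 / (0.90 + 0.086) = 0.913
- ρx = 0.20: 0.80 / (0.80 + 0.171) = 0.824

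Simulation at n = 1260, unadjusted against adjusted slope, agrees:
- ρx = 0: 0.301 and 0.301, ratio 1.00
- ρx = 0.05: 0.295 and 0.308, ratio 0.96
- ρx = 0.10: 0.290 and 0.316, ratio 0.92
- ρx = 0.20: 0.277 and 0.334, ratio 0.83

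Without a centre effect on the score, the false-positive rate stays at about 5–6%.

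**Step 2: false positives, when centre affects both assay and score and there is no true association.** The variance of the unadjusted slope is inflated by roughly 1 + (n/K − 1)ρxρy. With ρx = ρy = 0.10:
- n = 1260: 1 + (180 − 1) × 0.01 = 2.79
- n = 75: 1 + (10.7 − 1) × 0.01 = 1.10

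The problem therefore grows with patients per centre. Simulated rejection rates of the nominal 5% test without a centre term, by assay/score share:

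| Assay/score share | n = 75 | n = 900 | n = 1260 |
|---|---|---|---|
| 2% / 2% | 5% | 5% | 5% |
| 10% / 5% | 5–7% | 11% | 14% |
| 10% / 10% | 6% | 17% | 20–22% |
| 20% / 10% | 7% | 26% | 31–34% |

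Ranges in the last column are from separate runs. With centre as a fixed effect, the rate is 4–6% in every setting.

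**The case against.** The strongest objection is that this is detail for a statistical analysis plan, which is not at hand. The list is headed potential confounders, nothing excludes centre, and a centre term is commonly added later. This stands in part. It disposes of the CAT regression, for which the protocol states no covariate set. It does not dispose of the NHA regression, where the protocol chose to name an adjustment set and left out a recorded variable.

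Second, a reader might infer that the protocol itself says handling changes these assay results. It does not. The sentence concerns the original thrombin generation assay, is followed at once by the statement that the CAT has standardised most of it, and is not repeated for the NHA. Silence about the NHA is not evidence that it is sensitive.

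Third, a reader might infer that plasma is processed locally. The documents support drawing at centre visits only. They do not say where processing or assays take place, and section 5.1.2 refers biobank matters to regulations that are not shown.

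Fourth, every variance share above is assumed. With no centre contribution to the assay there is no dilution, and with 2% on each side the test keeps its level. It would therefore be wrong to say that the slopes are diluted, or that centre differences will pass for assay effects.

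Fifth, at n = 75 the false-positive rate is only about 5–7%, so the spurious-association argument has little force for the CAT.

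**Conclusion.** The point holds for the NHA association analysis, as a conditional weakness in a stated adjustment set. The omission is plain from the text. Its consequence depends on two quantities that the protocol does not give.

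If centre contributes 5–20% of NHA variance, about 4–17% of the slope is lost. If the bleeding score also varies by centre, the 5% test may reject too often. Over the assumed range, at 900 to 1260 patients, the rate runs from about 5% (2% shares on each side) to roughly 11–34% (assay 10–20%, score 5–10%). These figures assume seven equal centres.

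The route through factor consumption is plausible, because it is one of two equally scaled components of the score, but the documents do not demonstrate it.

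The point does not extend to the CAT regression as a defect, nor to the ROC and prediction analyses.

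**What to change.** In section 6.4.2, primary objective 1, add treatment centre as a fixed effect to the linear regression, alongside the listed genotype and VWF variables. Take centre from the sample collection form, and say how centres affected by the merger are coded.

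The cost is six degrees of freedom with seven centres (five with six), which is negligible at 900 to 1260 patients. No new data are needed.

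Leave the ROC and prediction analyses of 6.4.1 and 6.4.2 as they are. Centring assay values by centre would change the test being evaluated. Stratifying the 25-patient CAT severity groups by seven centres would leave 25/7, or about 3–4, patients per stratum. At most, report a sensitivity analysis there. For the CAT regression in 6.4.1, secondary objective 1, a centre term is optional.
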